2.6.2.3.2 Bone and renal biomarkers

Serum samples for bone and renal biomarkers will be collected from the patients participating in sub-study 2 at visits indicated in Table 6-1 of the study protocol.

Urine samples for bone and renal biomarkers from the patients participating in the sub-study will be assessed from 24h urine collection.

Table 2-5 Biomarkers

Category	Parameter(s)
Bone biomarkers	β -c-terminal telopeptide (β -CTX1), serum procollagen type 1 N-propeptide (sP1NP), intact parathyroid hormone (iPTH), 25-hydroxy vitamin D, 1,25 dihydroxy vitamin D, osteocalcin, oestradiol, Ca ²⁺ , Mg ²⁺ , phosphates (see also Table 6-4 of the study protocol)
Renal biomarkers	Serum cystatin C, urinary cystatin C (24h urine sample), urinary creatinine (24h urine sample), urinary albumin (24h urine sample),

For each biomarker in [Table 2-5](#), the test values and the change from baseline values will be summarized by visit and treatment group using n, mean, geometric mean and its 95% confidence interval, minimum, Q1, median, Q3, and maximum. The analyses will be performed in the SAF population.

2.6.2.4 Vital signs

Sitting systolic blood pressure (SBP), sitting diastolic blood pressure (DBP) and sitting pulse will be descriptively summarized (by n, mean, standard deviation, median, Q1, Q3, minimum and maximum) for actual value and change from baseline values for each scheduled assessment visit and treatment group. A listing of all patients with notable vital sign values and changes (as defined in [Table 2-6](#)) will be provided.

Table 2-6 Vital signs notable range deviations

Vital sign	Notable abnormalities	
Pulse (beats/min)		either ≥ 120 + increase $\geq 25^*$ or > 130 either ≤ 50 + decrease $\geq 30^*$ or < 40
BP (mmHg)	systolic	either ≥ 180 + increase $\geq 30^*$ or > 200 either ≤ 90 + decrease $\geq 30^*$ or < 75
	diastolic	either ≥ 105 + increase $\geq 20^*$ or > 115 either ≤ 50 + decrease $\geq 20^*$ or < 40

* Refers to post-BL value as compared to BL value.

2.6.2.5 ECG

The following variables will be descriptively summarized by visit and treatment: QTcF duration (msec), heart rate (beats/min), PR duration (msec), RR duration (msec), and QRS duration (msec).

The number and percentage of patients meeting the following criteria will be summarized by visit and treatment group for the double-blind period:

- QTcF > 500 msec
- QTcF > 480 msec
- QTcF > 450 msec
- QTcF increases from baseline \geq 30 msec
- QTcF increases from baseline \geq 60 msec
- PR > 200 and \leq 220 msec
- PR > 220 msec
- PR increases from baseline > 25% (PR > 200 msec)
- QRS > 110 and \leq 120 msec
- QRS > 120 msec
- QRS changes from baseline > 25 % (QRS > 110 msec)
- Heart rate > 100 beats/min
- Heart rate < 50 beats/min

In addition, a visit-based shift table will be provided to summarize the shifting from BL for each ECG parameter.

Cutoff points below are used to define normal or abnormal criteria in the above ECG shift table:

- QTcF: >450 or $=<$ 450 msec for male, or, >460 or $=<$ 460 msec for female
- QRS: >120 or $=<$ 120 msec
- PR: >200 or $=<$ 200 msec
- HR: >100 or $=<$ 100 beats/min

A listing of ECG parameters together with newly occurring or worsening abnormalities will be provided.

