### 4.1 Inclusion criteria

Patients eligible for inclusion in this study must fulfill all of the following criteria:

1. Written informed consent must be obtained before any assessment is performed.
2. Male or female outpatients,  $\geq 18$  years of age at Visit 1.
3.  $\text{BMI} \geq 22 \text{ kg/m}^2$  at Visit 1.
4. Type 2 diabetes with  $\text{HbA1c}$  between 6.5% and 10.0% at Visit 1.
5. Documented symptomatic chronic heart failure (NYHA II-IV) with at least one of the following symptoms at the time of Visit 1:
  - Dyspnea on exertion
  - Orthopnea
  - Paroxysmal nocturnal dyspnea
  - Peripheral edema
6. Plasma NT-proBNP  $> 300 \text{ pg/ml}$  at Visit 1.
7. Patients receiving ACEi, ARBs, MRAs, ARNi and/or  $\beta$ -blockers must be on a stable dose of these medications during the 1 month period prior to Visit 1.
8. Patients must be on diuretic therapy prior to Visit 1 (flexible dosing is permitted).
9. Controlled systolic BP defined as a target systolic BP less than 140mmHg; systolic BP up to and including 160mmHg if patient is on three or more medications to control BP, at randomization (Visit 201).
10.  $\text{eGFR} \geq 45 \text{ ml/min/1.73m}^2$  at Visit 1 (calculated by the Modification of Diet in Renal Disease formula (MDRD)).
11. Serum potassium  $\leq 5.3 \text{ mM}$  at Visit 1.

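### The ECG heart-rate shift table has only an upper cutoff, so rates below 50 bpm are labelled normal and no planned ECG summary table separates new from pre-existing low heart rate

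*SAP*

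**What the plan says.** SAP 2.6.2.5 (ECG) specifies four outputs that bear on heart rate.

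- **Descriptive summary.** Heart rate is summarised by visit and treatment. Change from baseline is not mentioned.
- **Threshold counts.** "The number and percentage of patients meeting the following criteria will be summarized by visit and treatment group for the double-blind period". For heart rate the criteria are above 100 bpm and "Heart rate < 50 beats/min". Neither depends on baseline. QTcF, PR and QRS each also have a criterion based on change from baseline.
- **Shift table.** The section says that "a visit-based shift table will be provided to summarize the shifting from BL for each ECG parameter" and then: "Cutoff points below are used to define normal or abnormal criteria in the above ECG shift table". The heart-rate line reads "HR: >100 or $=<$ 100 beats/min".
- **Listing.** "A listing of ECG parameters together with newly occurring or worsening abnormalities will be provided". What counts as an abnormality here is not defined.

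SAP 2.6.2.4 (Vital signs) covers sitting pulse separately. It gives descriptive statistics for actual values and change from baseline, and "A listing of all patients with notable vital sign values and changes" according to Table 2-6. The low-pulse rule in that table is a value of 50 or less with a decrease of at least 30 from baseline, or a value below 40.

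**The concern.** A shift table exists to show who moved from normal at baseline to abnormal on treatment. Here the rule that defines normal has no lower limit for heart rate, so a patient who goes from 72 to 45 bpm falls in the same cell as one who stays at 72.

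Elsewhere the SAP treats low rates as noteworthy. Section 2.6.2.5 counts rates below 50, Table 2-6 has low as well as high pulse limits, and the laboratory shift tables in 2.6.2.3.1 use low, normal and high. QTcF, PR and QRS have only upper limits throughout 2.6.2.5, so a single upper cut suits them. Heart rate is the one ECG parameter with criteria on both sides.

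The below-50 count does not fill the gap, because it mixes patients who became low with patients who were low already. Low rates at entry are plausible. Inclusion criterion 7 (Protocol 4.1) admits patients on beta-blockers and other heart-failure drugs, who "must be on a stable dose of these medications during the 1 month period prior to Visit 1", and Protocol 4.2 sets no numerical lower limit for heart rate. This is an inference; the documents do not state how common low baseline rates are.

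At stake is the readability of one safety display. Formal efficacy analysis was cut back after early termination (SAP 1 and 2.1), so descriptive safety tables make up much of the abbreviated report.

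**Working it through.** The plan gives no figure to reproduce. The check applies its rules to example pairs of baseline and on-treatment rates.

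**Rules used**

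- Shift table (SAP 2.6.2.5): abnormal if rate > 100, otherwise normal.
- Low count (SAP 2.6.2.5): counted if on-treatment rate < 50.
- Pulse listing (SAP Table 2-6, low side): listed if value ≤ 50 and baseline − value ≥ 30, or if value < 40. The same numbers are used as if pulse and ECG rate agreed.
- Three-level alternative from the SAP's own limits: low < 50, mid 50-100, high > 100.

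| Baseline → on treatment (bpm) | Shift table as written | In <50 count | Table 2-6 pulse listing | Three-level shift |
|---|---|---|---|---|
| 72 → 45 | normal → normal | yes | no (fall 27) | mid → low |
| 48 → 45 | normal → normal | yes | no (fall 3) | low → low |
| 85 → 48 | normal → normal | yes | yes (fall 37) | mid → low |
| 62 → 38 | normal → normal | yes | yes (below 40) | mid → low |
| 105 → 45 | abnormal → normal | yes | yes (fall 60) | high → low |
| 72 → 70 | normal → normal | no | no | mid → mid |

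**Reading the table**

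1. The first four rows and the last share one cell as written. Three of them are new low rates, one was low already and one is unremarkable.
2. The fifth row shows the other form of the problem: a fall to 45 from above 100 is tabulated as a return to normal.
3. The <50 count picks up all five low rates but treats 72 → 45 and 48 → 45 alike.
4. The pulse listing is narrower. For a value of 40 to 49 the baseline must be at least 30 higher, so the smallest baseline that can be flagged is 40 + 30 = 70. A patient with a baseline below 70 is not listed unless the pulse drops below 40.
5. With three levels, 72 → 45 and 48 → 45 fall in different cells, which is the separation that is missing.

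**What the crude count can still show**

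Let p be the proportion with baseline below 50, equal in expectation across randomised arms. Let n be the proportion newly low among patients who were not low at baseline, and s the proportion still low among those who were. In each arm the expected proportion below 50 is (1 − p)·n + p·s, so the difference between arms A and B is

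(1 − p)(n_A − n_B) + p(s_A − s_B).

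If s is the same in both arms, the crude difference is the difference in new low rates multiplied by (1 − p). It is diluted by the pre-existing cases, but it does not vanish unless nearly every patient was low at baseline.

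**The case against.** The strongest reply is that low heart rate is covered by other outputs and that the shift table's upper cut is a matter of layout.

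- The <50 count is given by visit and treatment group. Baseline low rates are balanced in expectation, so an arm that causes bradycardia would have a higher percentage. **This stands.** A reader might infer that a treatment difference in new bradycardia would stay hidden; the SAP does not support that, as the expression above shows.
- SAP 2.6.2.5 plans a patient listing of new or worsening abnormalities. **This stands in part.** It would be too strong to say that new and pre-existing low rates can never be told apart. But the listing is not a comparison by arm, and its abnormality is undefined. If it borrows the only normal/abnormal cutoffs in the section, rates below 50 are missed there too.
- SAP 2.6.2.4 summarises change from baseline in sitting pulse, including the minimum and first quartile, so the lower tail is visible by arm. **This stands**, but those statistics do not count patients newly below 50.
- Protocol 6.5.4 sends clinically significant ECG abnormalities to the adverse-event or medical-history forms as appropriate, and SAP 2.6.2.1 tabulates treatment-emergent events by arm. **This stands** for events that the investigator judges clinically significant.
- Cardiotoxicity, a predefined risk in SAP 2.6.2.2, is analysed through treatment-emergent adverse events. **This stands.** The shift table is not the designated instrument for that risk.

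The layout argument does not stand. The section says that its cutoffs define normal and abnormal. A rate below 50 therefore carries the label normal, a few lines after being named as a criterion to count.

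**Conclusion.** The point holds as a minor one. The heart-rate shift table labels all rates below 50 bpm as normal, and the <50 count ignores baseline. No planned ECG summary table therefore separates new from pre-existing low heart rate; that can be sought only in listings. The effect is confined to a descriptive safety output, with no bearing on the efficacy analyses or on any decision rule.

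The conclusion rests on reading the cutoffs as the complete definition for the shift table. Table shells are not among the documents, and a shell with a low category would remove the problem.

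No number of affected patients is given. A reader might try to size the issue by assuming a distribution of resting rates and taking the planned 124 patients in a large arm. The documents supply no heart-rate mean or SD. The planned arm size need not apply to a study that ended early, and the result would include patients who were already low at baseline.

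**What to change.** In SAP 2.6.2.5, replace the two-level heart-rate line for the shift table with three categories built from the section's own limits: below 50, 50 to 100, and above 100 bpm. Optionally, also report the <50 count by visit and arm among patients whose baseline rate was 50 bpm or more, with that group as the denominator.

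The cost is one changed line in the SAP and one extra category in the table program, plus one more row if the restricted count is added. No new data are needed, and neither the conduct of the trial nor any other analysis changes.

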2.6.2.6 Liver events

The liver event and laboratory trigger definitions are specified in the Appendix 2 of the study protocol. Liver event data will be listed.

The number and percentage of patients who meet the liver toxicity criteria in [Table 2-7](#) post baseline will be summarized by treatment group for the double-blind period. Listings of patients with clinically notable LFT values will be provided.

Table 2-7 Criteria for evaluating liver toxicity

Parameter	Criterion
ALT or AST	ALT or AST > 3xULN ALT or AST > 5xULN ALT or AST > 8xULN ALT or AST > 10xULN
Hy's category	ALT or AST >3x ULN and TBL >1.5x ULN ALT or AST > 3xULN & TBL > 2xULN ALT or AST > 5xULN & TBL > 2xULN ALT or AST > 8xULN & TBL > 2xULN ALT or AST > 10xULN & TBL > 2xULN ALT or AST > 3xULN & TBL > 2xULN & ALP ≤ 2xULN
TBL&ALP	TBL >1.5x ULN and ALP >2x ULN TBL >2x ULN and ALP >2x ULN
Isolated TBL	TBL >1.5x ULN & ALT and AST ≤3x ULN and ALP ≤2x ULN TBL >2x ULN & ALT and AST ≤3x ULN and ALP ≤2x ULN TBL >3x ULN & ALT and AST ≤3x ULN and ALP ≤2x ULN
Isolated ALP	ALP >1.5x ULN & ALT and AST ≤3x ULN and TBL ≤1.5x ULN ALP >2x ULN & ALT and AST ≤3x ULN and TBL ≤1.5x ULN ALP >3x ULN & ALT and AST ≤3x ULN and TBL ≤1.5x ULN ALP >5x ULN & ALT and AST ≤3x ULN and TBL ≤1.5x ULN

ALP: alkaline phosphatase; ALT: alanine aminotransferase; AST: aspartate aminotransferase; TBL: total bilirubin; ULN: upper limit of normal.

2.6.2.7 Renal events

The specific renal alert criteria and actions are defined in the Appendix 3 of the study protocol. Renal event data will be listed.

2.6.2.8 Other safety analyses (24h urinary calcium and phosphate excretion, bone mineral density (BMD))

Summary statistics (n, mean, standard deviation, median, Q1, Q3, minimum, and maximum) will be provided by visit and treatment for the 24h urinary calcium, 24h urinary phosphate excretion and BMD from sub-studies, for measurement at each visit and change from baseline values.

2.9 Interim analysis

Not applicable

3 Sample size calculation

The study planned to randomize approximately 496 patients in total, allocated in the ratio of 1:1:2:2:2 to the LIK066 2.5mg qd, 10mg qd, 50mg qd, empagliflozin and placebo treatment groups, respectively.

The following power calculations are based on the primary efficacy variable of log-transformed ratio of NT-proBNP at Week 12 to baseline. Due to the lack of available data in this patient population there is uncertainty on the standard deviation (SD) of the log-transformed ratio of week 12 to BL in NT-proBNP. Therefore calculations are provided for assumptions of SD in the range of 0.8, 0.85 to 0.9 to reflect the impact of this uncertainty on the power estimation. Based on the data from the PARAMOUNT HF study (data on file), a SD of 0.85 was considered a reasonable estimate.

Assuming a one-sided 2.5% significance level (with adjustments for multiple comparisons using the MCP-MOD), a sample size of approximately 496 patients (124 each in placebo and LIK high dose; 62 each in LIK low doses; 124 in empagliflozin that is not included in the dose-response modeling) will provide a mean power (over all candidate models) of 75%(or 90%) to detect a dose response signal, assuming that the underlying true maximum NT-proBNP reduction on LIK066 vs placebo is 25% (or 30%), and the standard deviation (on the log scale) is 0.85.

Table 3-1 Power for detecting a significant dose response signal*

Effect size for best dose	SD	Average power	Minimum power†
20%	0.8	58%	54%
20%	0.85	53%	49%
20%	0.9	48%	45%

Effect size for best dose	SD	Average power	Minimum power [†]
25%	0.8	80%	76%
25%	0.85	75%	71%
25%	0.9	70%	66%
30%	0.8	93%	91%
30%	0.85	90%	88%
30%	0.9	87%	84%

* Assumes 372 patients in LIK066 and placebo arms with effective sample size of 336 patients due to an effect of missing data equivalent to 10% fewer patients. Calculations were performed using the DoseFinding package in R.

† Power for a significant dose-response contrast test across all scenarios in Figure 2-1. The candidate model Emax with ED50 of 3mg has the lowest power.

Power consideration for assessing the glucose-lowering potential at Week 12

To explore the glucose-lowering potential of LIK066 vs. placebo or empagliflozin (EMPA), the treatment difference in HbA1c change from BL to Week 12 will be considered.

Table 3-2 Comparison of LIK versus placebo (at 2-sided alpha of 0.05)

	Expected treatment difference	SD	Power
LIK high dose (n=124) versus placebo (n=124)*	0.5%	1	96%
Any LIK low dose (n=62) versus placebo (n=124)*	0.5%	1	85%

*assuming 10% information loss due to drop-out.

Table 3-3 Comparison of LIK versus empagliflozin

	Expected treatment difference	SD	Probability of the 95% confidence interval upper bound < 0.4%
LIK high dose (n=124) versus EMPA (n=124)	0	1	84%
Any LIK low dose (n=62) versus EMPA (n=124)	0	1	68%

*assuming 10% information loss due to drop-out.

The calculations in Table 3-2 and 3-3 were performed using nQuery 7.0. No multiple testing adjustment was applied.

4 Change to protocol specified analyses

Due to the early termination of the CLIK066B2204 study, the following major changes to the protocol specified analyses have been made in the SAP amendment 1:

- “Week 12 Analysis” and “End of Study Analysis” as defined in the study protocol are no longer applicable. The analyses for the abbreviated CSR will be carried out after the completion of the study.
- MCP-Mod will not be performed for the primary endpoint change in log-transformed NT-proBNP at Week 12. Instead, MMRM will be performed as an exploratory analyses for NT-proBNP. See details in Section 2.5.
- Summary statistics will be provided for selected efficacy endpoints. All efficacy endpoints will be listed. See details in Sections 2.5, 2.6.1.2, 2.7.1.2.
- Subgroup analyses will only be performed for demographics and baseline characteristics, primary and key secondary efficacy endpoints summary statistics, AEs and AEs of special interest, in the subgroups LVEF <45% vs. >= 45%.

5 Appendix

The missing or partially missing AE start/end date and concomitant medication start/end date will be imputed using the Novartis ADaM Governance Board (AGB) global standard approach. Details will be provided in the study Programming Datasets Specifications.

5.1.1 Study drug

Any partial dates will be imputed as the earlier day of

- The last day in the month and
- The end day of the corresponding epoch

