2.1.1 General definitions

Study treatment, study medication or study drug

In this document, “study treatment”, “study medication” or “study drug” refers to the investigational, control drug or placebo of this study. Run-in study treatment, study medication or study drug refers to placebo matching LIK066/placebo matching Empagliflozin assigned to the patients during placebo run-in; double-blind study treatment, study medication or study drug refers to LIK066 2.5mg qd, LIK066 10mg qd, LIK066 50mg qd, Empagliflozin (up-titrated from 10mg qd to 25mg qd after 2 weeks) or placebo matching LIK066/placebo matching Empagliflozin assigned to a patient at randomization.

Run-in period

Run-in period refers to Epoch 2 (placebo run-in).

Double-blind period

Double-blind period refers to Epoch 3 (treatment period 1) + Epoch 4 (treatment period 2).

Baseline and study day

Baseline is defined as the last measurement obtained before or at the randomization visit. The first day of administration of randomized study treatment (first dose) is defined as Day 1 for the study. If the date of first administration is missing, then randomization date will be used as Day 1.

All other study days will be labeled relative to Day 1. For event dates on or after Day 1, study day for a particular event date is calculated as [Date of event] – [Date of first dose] + 1. For the dates before Day 1, study day for an event date is calculated as [Date of event] – [Date of first dose]. Duration of an event will be calculated as [Event end date] – [Event start date] + 1. The descriptor “Day 0” will not be used.

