2.4 Treatments (study treatment, rescue medication, concomitant therapies, compliance)

2.4.1 Study treatment / compliance

The duration of double-blind treatment exposure during double-blind period will be summarized by treatment group both descriptively in days (mean, standard deviation, minimum, Q1, median, Q3, and maximum) and by duration category in weeks (≤ 2 , $> 2-4$, $> 4-8$, $> 8-12$, $> 12-24$, > 24) for the SAF.

- Duration of exposure (days) = date of last dose of double-blind study drug – date of first dose of double-blind study drug + 1
- Duration of exposure (weeks) = (date of last dose of double-blind study drug – date of first dose of double-blind study drug + 1)/7

SAF will be used for the above analyses.

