2.6.2.1 Adverse events (AEs)

Treatment emergent adverse events (TEAEs) during the double-blind period are defined as any AE with start date on or after the start date of the first dose of the study drug during the double-blind period.

The number and percentage of patients with the following types of treatment emergent adverse events during the double-blind period will be provided by primary SOC, PT and treatment group

in separate tables: AEs, SAEs, AEs leading to study drug discontinuation, AEs suspected to be study drug related, and AEs leading to study drug interruption. TEAEs during the double-blind period will also be summarized by primary SOC, PT, maximum severity and treatment group. The most common TEAEs ($\geq 10\%$ in any treatment group) during the double-blind period will be presented by PT in descending order of frequency in the investigational study drug arm, LIK066 50 mg qd.

The following rules apply to the above AE summaries:

- If a patient has multiple AEs within a primary system organ class during the double-blind period, the patient will be counted only once in that primary system organ class
- If a patient has multiple occurrences of an AE with the same PT during the double-blind period, this patient will be counted only once at that PT level.
- An AE with increased severity should be considered and recorded as a new AE.

All TEAEs during the double-blind period will be summarized descriptively by primary SOC, PT and treatment in the following subgroups: baseline LVEF $< 45\%$ vs. $\geq 45\%$.

All AEs will be listed at the individual patient level. The listings will include those AEs reported during the screening and run-in period, and AEs reported after study discontinuation for those who discontinue the study prior to the end of the study.

Deaths occurred during the double-blind period will be summarized descriptively (using number and percentage of patients) by primary SOC and principal cause of death. All deaths will be listed.

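### Read literally, SAP 5.1.1 puts a first-dose date with a missing day at month end (or epoch end), up to 30 days late, and it is not reconciled with the randomisation-date rule in SAP 2.1.1

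*SAP*

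**What the plan says.** SAP 5.1.1, headed for study drug, consists of one rule: "Any partial dates will be imputed as the earlier day of" two candidates, "The last day in the month and" "The end day of the corresponding epoch". It names neither first-dose nor last-dose dates. The neighbouring sections are built differently. SAP 5.1.2 (adverse events) and 5.1.3 (concomitant medication) each give separate start and end rules, and each closes with a check that an imputed start does not fall after the end. SAP 5.1.1 has no such check.

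SAP 2.1.1 fixes the time origin: "The first day of administration of randomized study treatment (first dose) is defined as Day 1 for the study". It adds a fallback: "If the date of first administration is missing, then randomization date will be used as Day 1". It does not say whether a date with a known month and an unknown day counts as missing.

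Two safety definitions use the first-dose date directly. An event is treatment-emergent if it is "any AE with start date on or after the start date of the first dose of the study drug" in the double-blind period (SAP 2.6.2.1). Exposure in days is "date of last dose of double-blind study drug – date of first dose of double-blind study drug + 1" (SAP 2.4.1).

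**The concern.** The earlier of month end and epoch end is a natural upper limit for a stop date. For a start date it errs in one direction only: the imputed date is never before the true date and is usually after it. A wholly missing first-dose date would get a plausible Day 1 from SAP 2.1.1, while a date known to the month could be placed weeks late. Two programmers following the same SAP could derive different Day 1 values for the same patient.

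Day 1 or exposure feeds the treatment-emergent flag, exposure duration and its categories, the split between prior and concomitant medication (SAP 2.4.2), and the exposure-adjusted hypoglycaemia rates (SAP 2.6.2.2). Treatment start is also the reference date for imputing adverse event dates (SAP 5.1.2). After early termination only limited efficacy analyses remain (SAP 2.1), so the safety tables carry much of the abbreviated report.

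**Working it through.** The documents give no figure to reproduce, so the check applies the rules as date arithmetic.

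**Inputs.** Imputation rule: SAP 5.1.1. Day 1 and fallback: SAP 2.1.1. Exposure: SAP 2.4.1. Treatment-emergent definition: SAP 2.6.2.1. Adverse event start rule: SAP 5.1.2. Epoch 3 lasts 12 weeks = 84 days (protocol 3.1.3) and Epoch 4 lasts 24 weeks = 168 days (protocol 3.1.4), so the planned double-blind period is 84 + 168 = 252 days.

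**Assumptions.** Only the day of the first dose is missing. The true first dose is equally likely on each of the 730 days of two ordinary calendar years. Epoch 3 ends 84 days after first dose.

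**Size of the shift.** Shift = imputed date − true date. In a month of L days the shifts run from 0 to L − 1 and sum to L(L − 1)/2.
- Seven 31-day months: 7 × 465 = 3,255
- Four 30-day months: 4 × 435 = 1,740
- One 28-day month: 378
- Mean: (3,255 + 1,740 + 378)/365 = 5,373/365 = 14.7 days

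The range is 0 to 30 days, and the shift is 14 days or more for 54% of dates. It is zero only when the true date is the last of the month (24 of 730 dates, 3.3%). The epoch-end limit was the earlier date for none of the 730 dates, because month end is at most 30 days away. It would matter only for a patient whose epoch ended in the month of first dose.

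**As a share of exposure.**

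| Planned exposure | Mean loss | Largest loss |
|---|---|---|
| 84 days (Epoch 3) | 14.7/84 = 17.5% | 30/84 = 35.7% |
| 252 days (Epochs 3 and 4) | 14.7/252 = 5.8% | 30/252 = 11.9% |

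**Worked example.** The true first dose is 3 March, recorded as March with the day missing. The imputed Day 1 is 31 March, a shift of 28 days.
- Last dose 25 May: true exposure is 84 days (12 weeks, category >8–12). Imputed exposure is 56 days (8 weeks, category >4–8).
- Last dose 20 March, patient still in the epoch: true exposure is 18 days. Imputed exposure is 20 − 31 + 1 = −10 days. Protocol 5.6.2 keeps patients who stop drug in Epoch 3 under follow-up to the end of that epoch, so the epoch-end limit does not prevent this.
- Event with a complete start date of 10 March: treatment-emergent under the true date, not under the imputed one.
- Event starting in March with the day missing, ongoing: SAP 5.1.2 sets its start to the later of 1 March and 31 March + 1 day, which is 1 April. It stays treatment-emergent.
- The same event with a complete end date of 12 March: the end precedes the imputed treatment start, so the reference date becomes the earlier of consent and first visit. With that date taken as 3 February, the start becomes 1 March and the event is not treatment-emergent.

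**Partial last-dose date.** The error goes the other way: 25 May becomes 31 May, which adds 6 days of exposure.

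**Under the SAP 2.1.1 fallback.** With first dose on the day of randomisation, the shift is 0, exposure stays 84 days and the 10 March event stays treatment-emergent.

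**The case against.** The strongest reply is that SAP 5.1.1 never mentions first dose, that an epoch-end limit suggests stop dates were meant, and that SAP 2.1.1 has a specific rule for the first-dose date which may govern. This stands in part: the documents do not settle that Day 1 will be moved. But SAP 2.1.1 speaks of a missing date and SAP 5.1.1 of any partial one, so the specific rule does not clearly take over. The introduction to SAP section 5 refers to the programming specifications only for adverse event and concomitant medication dates.

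A reader might infer that the plan discards early adverse events. It does not: "All AEs will be listed at the individual patient level". Events can leave only the treatment-emergent tables, and only if they start in the gap. As the example shows, some partially dated events stay treatment-emergent. A reader might also infer that every affected patient's results are wrong. That is not so either: the shift can be zero, treatment-emergent status changes only for events in the gap, and medication status changes only if a medication stopped in the gap. Nor should the 18% be quoted alone, because SAP 2.4.1 summarises exposure over the whole double-blind period. Early termination will have shortened that period for some patients, by an amount the documents do not give.

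Partial first-dose dates should also be rare. Randomisation and the first drug pack are handled through the interactive system at Visit 201 (protocol 5.3), dosing is recorded on its own form (5.5.4), and automatic checks and queries apply (8.2, 8.3). This limits the reach but leaves the rule as it stands.

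**Conclusion.** The point holds as a minor defect in a stated rule. Applied as written to a first-dose date with a missing day, SAP 5.1.1 puts Day 1 late by 0 to 30 days, with the mean of about 15 days resting on evenly spread first-dose dates. Its overlap with SAP 2.1.1 is unresolved.

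The effect is confined to exposure, treatment-emergent status and the other safety summaries tied to Day 1. Baseline is tied to the randomisation visit (SAP 2.1.1), so the change-from-baseline efficacy results do not depend on it. The documents give no count of partial first-dose dates, so no trial-level effect can be stated.

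**What to change.** In SAP 5.1.1:

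1. Limit the month-end/epoch-end rule to last-dose dates and other study-drug stop dates.
2. Set a partial first-dose date to the later of the first day of the recorded month and the randomisation date. If the month is also missing, use the randomisation date. This agrees with SAP 2.1.1, which should cross-refer to it. If the true first dose was some days after randomisation, Day 1 may be placed early, which keeps events in the treatment-emergent tables.
3. Add a check that the imputed first dose is not after the last dose, matching the checks in SAP 5.1.2 and 5.1.3.

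The SAP should also say which rule applies to partial start dates of later dosing records, such as a restart after an interruption. These do not set Day 1.

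The cost is a few lines in the SAP and the matching lines in the dataset specification. No new data are needed.
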